1.2.2. Justification for design

The POISE trial has been designed to determine if HRT is superior to the COC on important clinical outcomes and patient-reported symptoms, based on the hypothesis that HRT provides more physiological continuous hormone supplementation with natural oestrogens⁶.

The outcomes being measured reflect that POI requires long-term treatment and differences in outcomes may not emerge for many months or even years, during which time adherence and outcomes will be affected by confounding factors e.g. pregnancy. Absolute BMD in the lumbar spine has been chosen as the primary outcome, as a survey of 242 patients indicated that osteoporosis was their most important concern, and protection against loss of BMD in the first years following diminishing ovarian activity is associated with a reduced risk of osteoporosis and fractures. Additionally, BMD measurement is accurate and reproducible, less likely to be affected by confounders than other measurements such as cardiovascular markers, easily available in clinical practice, and acceptable to patients.

The trial is powered to detect a small, but clinically significant, difference in the primary outcome at 90% power. It will also have reasonable power to determine small to moderate differences between

Trial name:	Premature Ovarian Insufficiency Study of Effectiveness of hormonal therapy	Protocol version:	4.0	date:	01 Oct 2024	Page:	18
-------------	--	-------------------	-----	-------	-------------	-------	----

the COC and oral HRT, between the COC and transdermal HRT, and between oral HRT and transdermal HRT (non-randomised comparison), dependent upon the proportion of women using HRT by each route.

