3.1. Trial Design

Multi-centre prospective, open, two-group parallel randomised controlled, superiority trial with equal allocation (1:1) to receive either HRT or the COC. Recruitment of 380 women is required to achieve ≥ 90% power to detect a difference in mean of 0.05 g/cm² in lumbar spine BMD between HRT and the COC. Further information on sample size and randomisation can be found in Section 6 and Section 13.

Participants will start treatment according to their randomised treatment allocation. Long-term systemic hormone treatment is recommended at least until the age of natural menopause. For the purpose of this trial, participants will be advised to remain on their allocated treatment for a minimum duration of 2 years, however it is acknowledged that a number of factors may influence a participant’s choice of therapy over this time.

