13.1.1. Power Calculations / sample size calculation

The original sample size was powered to detect a mean difference in lumbar spine BMD (g/cm²) of 0.05 between the HRT and the COC group at 2 years post-randomisation to ensure that the trial preserves at least the effect observed in a similar previous study¹⁷. This target difference also represented an absolute change thought to be the least significant change in spine BMD that is unlikely to be due to the precision error of the test. The precision error is best described using the smallest detectable difference, rather than the coefficient of variation, and for lumbar spine a change of BMD of at least +/-0.05g/cm² is considered clinically significant^{39,40}. Assuming that the lumbar spine BMD in each group varies with a standard deviation (SD) of 0.15, observed from 112 comparable patients in an unpublished cohort of POI women and the previous trial¹⁷, a total of 382 patients (191 per group)

Trial name:	Premature Ovarian Insufficiency Study of Effectiveness of hormonal therapy	Protocol version:	4.0	date:	01 Oct 2024	Page:	42
-------------	--	-------------------	-----	-------	-------------	-------	----

were required to detect the between-group difference of 0.05 g/cm² (a small effect size of 0.333) with a 90% power, 5% 2-sided significance level and 1:1 allocation. Attrition had been a major problem in studies of similar population, so we allowed for up to 20% loss to follow-up, requiring 480 patients to be recruited.

This sample size was expected to still have >80% power to detect a medium effect size (between-group mean difference of 0.075 g/cm², SD=0.15) between each HRT route (oral or transdermal) and the COC, assuming the proportion in one route is between 20% to 50%.

The above sample size was calculated without accounting for correlation between repeated outcome measures. At the design stage, it was decided not to account for the repeated measures design in the sample size calculation to be conservative as it was assumed that the efficiency gained by repeated measures would be offset by possible efficiency loss attributable to misspecification of any of the sample size parameters due to uncertainty about the assumptions.

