At a review after 18 months of recruitment it was recommended by the Trial Steering Committee (TSC) that the sample size should be readjusted to account for the correlation between repeated outcome measures. No outcome data was available to the TSC or investigators when the decision was made. The revised sample size uses the same parameters as the original sample size calculation but are based on a mixed-effect model analysis of repeated measures data including a baseline and two repeated post-randomisation outcome measurements, with contrasts to assess treatment effects at each time point. The calculation assumes a compound symmetry covariance structure (exchangeable), with a common variance (σ^2) for the outcome measure and a common correlation (ρ) between repeated follow-up assessments (autocorrelation). For each value of σ^2 , the required sample size increases with the correlation ρ between follow-up measures such that a correlation of 1 gives a sample size equivalent to two-sample t-test. A value of $\rho=0.4$ to 0.6 is typical in many studies. At the time of the review, there was insufficient accrued data to calculate the autocorrelation, so a conservative autocorrelation between follow-up measures of 0.6 was chosen. The sample size required for analysis to estimate the same effect as the original calculation, with 90% power, is 304. Allowing for 20% loss to follow-up requires the recruitment of 380 participants. To achieve 80% power and allowing for 20% loss of primary outcome data, 286 participants would be required.

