13.3. Analysis of Outcome Measures

The analysis and reporting of the trial will be in accordance with CONSORT guidelines. A full statistical analysis plan (SAP) will be developed and agreed prior to database lock for the analysis of the primary outcome at 2 years.

Trial name:	Premature Ovarian Insufficiency Study of Effectiveness of hormonal therapy	Protocol version:	4.0	date:	01 Oct 2024	Page:	43
-------------	--	-------------------	-----	-------	-------------	-------	----

Appropriate descriptive statistics (mean, standard deviation, median, lower and upper quartiles, minimum, maximum or frequencies and percentages) for the demographic and clinical outcome measures at baseline will be used to assess balance between the randomised arms at baseline, but no formal statistical comparisons will be performed. Baseline characteristics will also be descriptively compared between those randomised and those analysed to see if the attrition has introduced any imbalances. Descriptive statistics appropriate for the outcome will also be presented for all outcomes at all collected time points by treatment group.

The primary comparative analysis will be based on intention-to-treat, analysing participants in the groups to which they were randomised. The evaluation of the primary outcome of BMD in the lumbar spine at 2 years will be performed using a mixed effects model to allow for all available follow-up data (1 year, 2 year) to be used, adjusted for the baseline BMD in the lumbar spine and the minimisation variables as fixed effects except site which will be entered as a random effect. The model will include a treatment by time interaction to obtain the estimates of treatment effect at each follow-up time, with 2 years being the primary evaluation. An interaction between each covariate and time will be added to get a different adjustment for each covariate at each time point. The estimated between group effect will be presented using the difference in means, with a 95% confidence interval. The primary treatment comparison will be the contrast between allocated treatment groups at 2 years.

Sensitivity analyses for the primary outcome will include:

- Complete case analysis based on observed outcome data at 2 years
- Use of multiple imputation with auxiliary variables (if applicable) not included in the primary analysis also included in the imputation model.

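### The revised sample size of 304 evaluable (380 recruited) is derived for the average of the 1-year and 2-year BMD values, not for the 2-year contrast that is primary, so it does not support the stated 90% power

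*Protocol*

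**What the plan says.** Section 13.1.1 first gives the original calculation. Lumbar spine BMD "varies with a standard deviation (SD) of 0.15", and 382 evaluable women (191 per group) were "required to detect the between-group difference of 0.05" g/cm² at 2 years with 90% power at two-sided 5%. Allowing for 20% loss, this became 480.

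The revision keeps those parameters. It describes a mixed model with a baseline and two follow-up measurements, compound symmetry, and contrasts at each time point. It says the required number grows with the correlation between follow-ups, "such that a correlation of 1 gives a sample size equivalent to two-sample t-test". No data were available to estimate that correlation, "so a conservative autocorrelation between follow-up measures of 0.6 was chosen". The result is: "The sample size required for analysis to estimate the same effect as the original calculation, with 90% power, is 304". With 20% loss this is 380; the 80% power variant is 286 recruited. Section 3.1 repeats the claim ("Recruitment of 380 women is required to achieve" at least 90% power), and the Trial Summary carries the same 304 and 380.

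Section 13.3 fixes the analysis: "The primary treatment comparison will be the contrast between allocated treatment groups at 2 years". The model adjusts for baseline BMD and includes a treatment-by-time interaction and an interaction of every covariate with time. The effect averaged over the 2 years is listed only as a supplementary analysis.

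For the HRT routes, section 13.1.1 quotes more than 80% power at 0.075 g/cm² (0.5 SD) for the original size. Section 1.2.2 still says of the current trial: "It will also have reasonable power to determine small to moderate differences between" the COC and each HRT route.

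**The concern.** The described behaviour of the sample size, rising with the correlation between follow-ups and reaching the t-test value at a correlation of 1, belongs to the mean of several follow-up values. Averaging two imperfectly correlated values reduces variance, and the gain disappears as they become identical. A contrast at a single visit does not behave this way. When treatment and all covariates interact with time and the data are complete, the 1-year value does not reduce the variance of the 2-year contrast, whatever its correlation with the 2-year value. The correlation that does reduce it is the one between baseline and 2 years, and it acts in the opposite direction: the higher it is, the fewer women are needed. The calculation does not use it.

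The reduction of 100 women rests on this calculation, and the 90% figure is repeated as the trial's headline power. As written, the justification supports a supplementary estimand rather than the primary one.

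**Working it through.** **Inputs** (section 13.1.1): difference δ = 0.05, SD σ = 0.15, two-sided 5%, 90% power, 1:1 allocation, two follow-ups, correlation between them ρ = 0.6, 20% loss. The baseline-to-2-year correlation r is not stated, so it is treated as an assumption and varied.

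**1. Original figure.** n per group = 2(z₀.₉₇₅ + z₀.₉₀)²σ²/δ² = 2 × (1.960 + 1.2816)² × 9 = 189.1, so 380 in total. The t-based version gives 382, as stated.

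**2. Revised figure.** The variance of the mean of two equally correlated values is σ²(1 + ρ)/2, a factor of 0.8. Then 189.1 × 0.8 = 151.3, so 152 per group, 304 in total, and 304/0.8 = 380. Both match exactly. At 80% power, 141.3 × 0.8 = 113.0, so 114 per group, 228 in total and 285 recruited (286 stated). The base is the z-based 189.1; starting from 382 would give 305.6.

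**3. Other routes to 304.** With ρ = 0.6 as the common correlation, a 2-year ANCOVA gives 244, a baseline-adjusted time average 168, and a time-averaged change score 228. A single-visit change score also gives 304, because 2(1 − 0.6) = 0.8. Its sample size, however, falls as ρ rises and is zero at ρ = 1, which is the reverse of what section 13.1.1 describes. Only the time average fits both the number and the description.

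**4. What 304 gives for each contrast.** Generalised least squares, 152 per group, complete data, treatment-by-time model, no baseline:

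| Contrast | SE | Power |
|---|---|---|
| 2 years (primary) | 0.15 × √(2/152) = 0.01721, for any ρ | 82.8% (82.6% t-based) |
| Mean of 1 and 2 years | 0.01721 × √0.8 = 0.01539 | 90.1% |

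Without credit for baseline, 90% power at 2 years needs 380 (z) or 382 (t) evaluable women.

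**5. Incomplete 2-year data.** As a best case, suppose all 190 per group have a 1-year scan and 152 have a 2-year scan. The variance of a group's 2-year mean is then σ²[(1 − ρ²)/152 + ρ²/190]. At ρ = 0.6 the SE of the difference is 0.0166 and the power 85.5%.

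**6. Credit for baseline.** The 2-year variance becomes σ²(1 − r²). All values of r are assumptions:

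| r | Power at 304 | Evaluable for 90% |
|---|---|---|
| 0 | 82.8% | 380 |
| 0.3 | 86% | 346 |
| 0.45 | 90% | 302 |
| 0.6 | 95% | 244 |
| 0.8 | 99.8% | 138 |

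Break-even: r = √(1 − 152/189.1) = 0.44.

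**7. Route contrast.** At 0.5 SD with 20% of the HRT group on one route, 30.4 women face 152 on the COC. The SE in SD units is √(1/30.4 + 1/152) = 0.199, and 0.5/0.199 − 1.96 = 0.56, so power is about 71% with no baseline credit. The same calculation at 382 evaluable gives about 80%, in line with the figure that section 13.1.1 quotes for the 480 target.

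**The case against.** The strongest reply is that no shortfall has been shown. The primary model adjusts for baseline lumbar spine BMD, and the 83% applies only if baseline tells us nothing about BMD at 2 years. Once r reaches about 0.45, 304 women give 90% or more. This stands. A reader might infer from the mismatch that the trial is underpowered or that 380 is too few; the documents do not support that, because they give no value of r.

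Second, the statement that the 1-year scan adds nothing is exact only for complete data, and 20% loss is expected. This also stands, but the best case at ρ = 0.6 is 85.5%, still short of 90%. The site random effect breaks exact equality with a 2-year-only analysis too, but changes the SE by only about 0.3%.

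Third, 0.6 is the upper end of the range the protocol calls typical, and so the cautious end under its own formula. That is fair. A reader might argue from the precision-error remarks in section 13.1.1 that the true correlation must be far higher. The protocol does not give the definition needed to turn its smallest detectable difference into a correlation, and measurement repeatability is not the same as correlation over a year of treatment. The objection to 0.6 is that it is not the parameter that governs the 2-year contrast.

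Fourth, the figure of more than 80% for the routes is tied to the original size, and section 1.2.2 gives no number and makes power depend on route uptake. So no current figure is false. With baseline credit, the 71% becomes about 80% at r = 0.45 and 88% at r = 0.6. What remains is that the claim was not restated after the reduction.

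A reader might also infer that the wrong formula will mislead the month-36 review. Section 13.3.2 limits that review to recruitment, retention and adherence, and plans no re-estimation of correlation.

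**Conclusion.** The justification is wrong; the target of 380 may well be adequate. The 304 is the sample size for the mean of years 1 and 2, while the primary comparison is at 2 years. On the protocol's own inputs with no baseline credit, 304 gives about 83% power for that comparison, rising to at most about 85.5% at ρ = 0.6 under the most favourable pattern of loss. Whether the trial reaches 90% depends on a baseline-to-2-year correlation that the protocol never states, with break-even at about 0.44 to 0.45. These figures assume SD 0.15, a difference of 0.05 and 152 evaluable women per group; the values of r are assumptions.

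**What to change.** Keep the target of 380. In the Trial Summary, section 3.1 and section 13.1.1:

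- Replace the justification with a 2-year ANCOVA calculation, n per group = 2(z_α/2 + z_β)²σ²(1 − r²)/δ², with a stated r and its source, and show power at 304 evaluable over a range of r, including r = 0.
- Delete the statements that the sample size rises with the correlation between follow-ups to the t-test value, and that 0.6 is conservative. Neither applies to the 2-year contrast.
- Restate the route-contrast power at 304 (about 71% at 0.5 SD with a 20% share and no baseline credit), and align section 1.2.2 with it.

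Optionally, estimate r and the SD from pooled blinded data. This would be a small added task, since no planned review includes it.

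The cost is protocol and SAP wording, with no extra participants. The downside is that the quoted power becomes conditional on r.

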13.2. Definition of Outcome Measures

13.2.1. Primary outcome measures

The primary outcome is absolute BMD (g/cm²) at 2 years from the date of randomisation assessed by a standard DEXA scan of the lumbar spine.

13.2.2. Secondary outcome measures

The secondary outcomes will be measured at different stages throughout the trial. Further information can be found in Section 2.2.2.

13.3. Analysis of Outcome Measures

The analysis and reporting of the trial will be in accordance with CONSORT guidelines. A full statistical analysis plan (SAP) will be developed and agreed prior to database lock for the analysis of the primary outcome at 2 years.

Trial name:	Premature Ovarian Insufficiency Study of Effectiveness of hormonal therapy	Protocol version:	4.0	date:	01 Oct 2024	Page:	43
-------------	--	-------------------	-----	-------	-------------	-------	----

Appropriate descriptive statistics (mean, standard deviation, median, lower and upper quartiles, minimum, maximum or frequencies and percentages) for the demographic and clinical outcome measures at baseline will be used to assess balance between the randomised arms at baseline, but no formal statistical comparisons will be performed. Baseline characteristics will also be descriptively compared between those randomised and those analysed to see if the attrition has introduced any imbalances. Descriptive statistics appropriate for the outcome will also be presented for all outcomes at all collected time points by treatment group.

The primary comparative analysis will be based on intention-to-treat, analysing participants in the groups to which they were randomised. The evaluation of the primary outcome of BMD in the lumbar spine at 2 years will be performed using a mixed effects model to allow for all available follow-up data (1 year, 2 year) to be used, adjusted for the baseline BMD in the lumbar spine and the minimisation variables as fixed effects except site which will be entered as a random effect. The model will include a treatment by time interaction to obtain the estimates of treatment effect at each follow-up time, with 2 years being the primary evaluation. An interaction between each covariate and time will be added to get a different adjustment for each covariate at each time point. The estimated between group effect will be presented using the difference in means, with a 95% confidence interval. The primary treatment comparison will be the contrast between allocated treatment groups at 2 years.

Sensitivity analyses for the primary outcome will include:

- Complete case analysis based on observed outcome data at 2 years
- Use of multiple imputation with auxiliary variables (if applicable) not included in the primary analysis also included in the imputation model.
- Adjustment for any other baseline variable (if applicable) with marked imbalance between the two treatment groups

Supplementary analyses for the primary outcome will investigate potential effects of compliance with allocated treatment using complier average causal effect (CACE) analysis (or per-protocol analysis should there be high crossover rates making CACE identification impossible) and estimate an overall time-averaged between-group effect over the 2 years to compare the overall rate of change in BMD between groups.

Main analyses of secondary outcomes will be based on intention-to-treat, analysing participants in the groups to which they were randomised, regardless of adherence with allocation. Sensitivity analyses (as described for the primary outcome) may also be performed for key secondary outcomes such as blood pressure, MENQOL-I, and BMD at 1 year and 2 years. Ordered logistic regression models will be used to compare the total lumbar spine and hip T-score categories (≤ -2.5 , > -2.5 to ≤ -1 , > -1) between groups, adjusted for the minimisation variables; however, should there be only a small number of participants in one of the categories then categories will be collapsed into two for analysis and logistic regression used. Between-group comparison of secondary outcomes will be based on an appropriate regression for the outcome adjusted for the minimisation variables and baseline outcome measure for continuous variables if available. For repeated measures, appropriate mixed-effect models for the outcome (linear for continuous outcomes and logistic for binary), adjusted for the minimisation variables, will be used to estimate the difference between groups at each time point. Supplementary analysis of key secondary outcomes may also be conducted according to actual treatment used if the percentage of women who stop using their allocated treatment or switch to the other treatment is high.

Adverse events will be presented descriptively only and will be summarised according to both the allocated group and the treatment received.

Trial name:	Premature Ovarian Insufficiency Study of Effectiveness of hormonal therapy	Protocol version:	4.0	date:	01 Oct 2024	Page:	44
-------------	--	-------------------	-----	-------	-------------	-------	----

Mixed-effect models, with similar adjustments as described for analysis of the primary outcome, will be used to compare BMD and key secondary outcomes between each route of HRT administration (oral and transdermal) HRT and COC and between oral HRT and transdermal HRT (non-randomised comparison). Key secondary outcomes to be compared will be specified in the SAP.

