2.2. Outcome Measures

2.2.1. Primary outcome:

Absolute BMD (g/cm²) at 2 years from the date of randomisation, assessed by a standard DEXA scan of the lumbar spine.

2.2.2. Secondary outcomes:

The secondary outcomes will be measured at different stages throughout the trial.

- Absolute BMD (g/cm²) in lumbar spine at 1 and 2 years.
- Absolute BMD (g/cm²) in hip at 1 and 2 years.
- T-score category (≤ -2.5 , > -2.5 to ≤ -1 , > -1) for BMD at lumbar spine at 1 and 2 years.
- T-score category for BMD at hip at 1 and 2 years.

Trial name:	Premature Ovarian Insufficiency Study of Effectiveness of hormonal therapy	Protocol version:	4.0	date:	01 Oct 2024	Page:	20
-------------	--	-------------------	-----	-------	-------------	-------	----

- Individual domains (vasomotor, psychosocial, physical and sexual) and summary score of Menopause Specific Quality of Life (MENQOL-I)-Intervention questionnaire at 3, 6 and 12 months then annually.
- Sexual function (pleasure, discomfort and frequency) measured by the Sexual Activity Questionnaire (SAQ)² at 3, 6, 12 months then annually.
- Work Productivity (absenteeism, presenteeism, work productivity loss and activity impairment), using the Work Productivity and Activity Impairment (WPAI) Scale (Specific health Problem)³ at 3, 6, 12 months then annually.
- Weight (kg) at 3, 6, and 12 months then annually.
- Systolic blood pressure (mm Hg) at 3, 6 and 12 months then annually.
- Diastolic blood pressure (mm Hg) at 3, 6 and 12 months then annually.
- Pregnancy and pregnancy outcome.
- Satisfaction with treatment, on a 5-point Likert scale at 3, 6 and 12 months then annually.
- Change or cessation of treatment at 3, 6 and 12 months then annually.
- Adverse events at 3, 6 and 12 months and then annually. Specific minor-side effects collected will include breast pain, nausea, headaches, skin or hair changes and unscheduled bleeding (see Section 9.2) as well as more serious events such as venous thromboembolism. All serious adverse events will be collected and causal relationship with treatment considered.
- Diagnosis of cancer, cardiovascular disease, cognitive impairment, bone fractures and mortality will be collected from routine data sources up to 5 years.

Sub-study

- Bone metabolism markers, liver function tests, bone profile, and 1,25 Vitamin D. Blood and urine samples will be collected in a subset of participants from selected sites, at baseline, 3 and 12 months (not reported until the end of the study).

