After informed consent (and if required a washout period), baseline data will be collected by a member of the site research team and the participant will be enrolled using the online trial randomisation system. All participants are required to have had a DEXA bone density measurement of lumbar spine and hip in the 6 months prior to randomisation. Further information on baseline data collection requirements is detailed in Section 8.2.

An authorised member of the site research team will then log into the secure randomisation system and randomise the participant.

6.2.Randomisation

Eligible women will be individually randomised on a 1:1 ratio to one of the treatment groups using an online randomisation system developed and maintained by the NCTU. Access to the system will be granted by the NCTU in accordance with the roles delegated by the Principal Investigator on the Site Delegation Log.

Treatment will be assigned using a minimisation algorithm balancing on the following factors:

- Recruiting site
- Age at randomisation (≥ 18 - < 25 years or ≥ 25 - < 40 years)
- Body mass index (< 25 kg/m² or 25 - < 30 kg/m² or ≥ 30 kg/m²)
- Smoking status (quit smoking/never smoked or current smoker)
- Previous oestrogen treatment (Yes or No)

The minimisation algorithm will include a probabilistic element to allocation, making prediction of the allocated group virtually impossible.

For women randomised to HRT, participant preference will be taken into account when deciding which route of administration, oral or transdermal, to be used. Where there is no preference, the route will be randomly selected using an online randomisation system.

Trial name:	Premature Ovarian Insufficiency Study of Effectiveness of hormonal therapy	Protocol version:	4.0	date:	01 Oct 2024	Page:	25
-------------	--	-------------------	-----	-------	-------------	-------	----

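### The T-score category models omit baseline BMD, although it is measured in every woman and the primary model for the same scan adjusts for it

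*Protocol*

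**What the plan says.** Section 13.3 (Analysis of Outcome Measures) fixes both the model and the covariates for the T-score outcomes. It states "Ordered logistic regression models will be used to compare the total lumbar spine and hip T-score categories", with the comparison "between groups, adjusted for the minimisation variables; however, should there be only a small number" in one of the categories, the outcome is to be reduced to two categories and analysed by logistic regression.

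The next sentence gives the general rule for secondary outcomes: regression "adjusted for the minimisation variables and baseline outcome measure for continuous variables if available". The sentence after it, on repeated measures, again names only the minimisation variables: models "adjusted for the minimisation variables, will be used to estimate the difference between groups at each time point".

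For the primary outcome the same section does the opposite. The mixed model is "adjusted for the baseline BMD in the lumbar spine and the minimisation variables as fixed effects", with site as a random effect.

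Three other places bear on this:
- Section 6.1 makes the baseline scan compulsory: "All participants are required to have had a DEXA bone density measurement of lumbar spine and hip in the 6 months prior to randomisation".
- Section 6.2 lists the minimisation factors as site, age, BMI, smoking status and previous oestrogen treatment. Neither BMD nor T-score is among them.
- Section 2.2.2 lists T-score category as a secondary outcome at the lumbar spine at 1 and 2 years, and likewise "T-score category for BMD at hip at 1 and 2 years".

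**The concern.** A three-category T-score is not a continuous variable, so under the stated rule it gets no baseline term. No other sentence supplies one, and BMD does not enter through the minimisation factors. The protocol thus treats baseline BMD as worth adjusting for when the follow-up reading is continuous and drops it when the same reading is cut into categories.

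Baseline is the same measurement at the same skeletal site, so it can be expected to be the best single predictor of the follow-up category. The documents do not say this, but it follows naturally from what they measure. Categorising BMD already loses information, and omitting baseline loses more at no saving in data or cost.

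Four comparisons are affected: spine and hip at 1 and 2 years. Two things are at stake. Power is lower than the collected data allow. The result is also exposed to chance imbalance in baseline BMD, so a T-score result could appear to disagree with the baseline-adjusted BMD result from the same scans.

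The covariate set is written into the protocol. It is not a detail left for the SAP, and a SAP that follows the protocol would carry the omission forward.

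**Working it through.** **Inputs from the protocol (section 13.1.1).** Difference 0.05 g/cm², SD 0.15, two-sided 5%, 1:1 allocation, 304 women analysed, 380 recruited.

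**The plan's own figures.**
- Original size: per arm 2 × [0.15 × (1.960 + 1.282) / 0.05]² = 189.1. With the t distribution this is 190.1, so 191 per arm and 382 in total, as stated. 382 / 0.8 = 478, against a stated 480 (rounding).
- Revised size: 189.1 × (1 + 0.6) / 2 = 151.3, so 152 per arm, 304 in total, and 304 / 0.8 = 380, as stated.
- 80% power: 113.02, so 114 per arm, 228 in total, and 228 / 0.8 = 285, against a stated 286.

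The inputs are therefore read correctly. The protocol states no power for the T-score outcomes.

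**Simulation of the T-score comparison.** A three-category proportional-odds model with cut-points -2.5 and -1 was fitted with and without continuous baseline BMD. The test was a two-sided 5% likelihood-ratio test, with 600 simulated trials per scenario and N = 304. Three assumptions are not in the documents:
- a reference SD of 0.12 g/cm² for the T-score, giving a T-score SD of 0.15 / 0.12 = 1.25;
- a mean T-score of -0.5, -1 or -1.5 in the lower arm;
- the baseline-to-2-year correlation ρ.

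The minimisation variables were left out of both models.

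| Mean T-score | ρ | Power without baseline | Power with baseline |
|---|---|---|---|
| -1 | 0 | 70% | 69% |
| -1 | 0.4 | 70% | 77% |
| -1 | 0.6 | 69% | 83% |
| -1 | 0.8 | 70% | 95% |
| -1 | 0.9 | 67% | 98% |
| -0.5 | 0.4 | 59% | 65% |
| -0.5 | 0.6 | 61% | 76% |
| -0.5 | 0.8 | 61% | 88% |
| -1.5 | 0.4 | 72% | 78% |
| -1.5 | 0.6 | 72% | 87% |
| -1.5 | 0.8 | 74% | 98% |

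The Monte Carlo standard error near 70% is √(0.7 × 0.3 / 600) = 1.9 points. This explains the small movement in the column without baseline, which does not truly depend on ρ. Under no treatment effect (ρ = 0.9) the rejection rates were 5.7% without and 4.8% with baseline, both consistent with 5%. Repeat simulations at the same sample size, effect and cut-points gave 68–72% v 84% at ρ = 0.6, 68–73% v 94–95% at 0.8, 70–71% v 99% at 0.9, and 76% v 80% at 0.4.

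**What ρ is plausible?** The protocol's 0.6 is a correlation between follow-up measures, not between baseline and follow-up. Section 13.1.1 also equates 0.05 g/cm² with the smallest detectable difference for the spine. If that is the usual 95% limit for the difference between two readings, the measurement error SD is 0.05 / (1.96 × √2) = 0.018. Against a total SD of 0.15, reliability is 1 − (0.018 / 0.15)² = 0.986. Real change over two years lowers the correlation below this ceiling, but measurement error alone does not keep it low.

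**Chance imbalance.** With SD 0.15 at baseline and 304 women, the standard error of the between-arm baseline difference is 0.15 × 2 / √304 = 0.017 g/cm². The 95% range is ±1.96 × 0.017 = ±0.034, about two-thirds of the 0.05 target. At ρ = 0.6, 0.6 × 0.034 = 0.020 g/cm² of an imbalance of that size carries through to follow-up.

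**The case against.** The strongest reply is that little inference is lost. T-score category is a coarsened form of BMD, and continuous BMD at both sites is analysed with baseline adjustment: the spine in the primary model, the hip under the rule for continuous outcomes. The category analysis restates that result on a clinical scale. It is secondary, no power is claimed for it, and its type I error is sound. All of this is true and limits the weight of the point. It is not a reason for leaving baseline out of a model that will still be fitted and reported.

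Second, the size rests on figures the protocol does not give. Section 13.1.1 calls correlations of 0.4 to 0.6 between repeated follow-up measures typical, and at 0.4 the gain is about 6 points. Leaving out the minimisation variables may overstate the gain if BMI, age or previous oestrogen treatment predict BMD. The effect size is the 2-year spine target, and the documents give no hip SD and no 1-year or hip target difference. These points stand: the direction is secure, but the figures are illustrative and apply directly to the spine at 2 years only.

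Third, section 13.3 has a sensitivity analysis for marked baseline imbalance. It is written for the primary outcome and only may be extended to key secondary outcomes. T-score category is not among the examples, so it does not fill the gap.

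Fourth, the adjusted odds ratio estimates a different quantity from the unadjusted one, because odds ratios are non-collapsible. That is correct and must be disclosed.

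**Conclusion.** The concern holds. The protocol specifies T-score category models without the baseline measurement, which every participant must have and which the primary model uses for the same spine scan.

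The fault is lost efficiency and inconsistency, not bias or an inflated error rate. At 304 women and 0.05 g/cm², the cost at the 2-year spine comparison is about 6 power points at a baseline-to-follow-up correlation of 0.4, 13 to 15 at 0.6, and 23 to 27 at 0.8 across the assumed mean T-scores. There is no cost at zero correlation. These figures rest on the assumed T-score mean and reference SD, on models without the minimisation variables, and on a correlation the documents do not report. The same direction is expected for the hip and for 1 year, but it was not quantified there.

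The change should be made, though the trial's primary conclusion does not depend on it.

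**What to change.** In section 13.3, and in the SAP before the 2-year database lock, state that the ordered logistic models for T-score category adjust for the minimisation variables and for baseline T-score or BMD at the same skeletal site, entered as a continuous covariate. State that the same covariate is kept if the categories are collapsed and logistic regression is used, and in any repeated-measures form of the model.

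Extend the general rule so that baseline adjustment is not confined to continuous outcomes but covers categorical or binary outcomes that have a baseline measurement. This extension follows the same reasoning but was not quantified here.

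State that the resulting odds ratio is conditional on baseline, and report the observed category proportions by arm beside it.

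The cost is a change of wording and this change in the meaning of the odds ratio. No new data are needed, because the baseline scan is already an entry requirement.
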